7.1.3. Other Concomitant Medications

To the extent possible, administration of any prescription or over-the-counter drug products other than study medication should be minimized during the study period. Patients should be discouraged from use of "health supplements" (eg, creatine, glutamine, coenzyme Q), herbal remedies, growth hormone, self-prescribed drugs, street drugs, tobacco products, or alcohol at any time during the study. Caution should be exercised during concomitant use of study drug and potentially nephrotoxic agents.

If considered necessary for the patient's well being, drugs for concomitant medical conditions or for symptom management may be given at the discretion of the investigator. The decision to authorize the use of any other drug(s) should take into account patient safety, the medical need, the potential for drug interactions, the possibility for masking symptoms of a more relevant underlying event, and whether use of a concomitant medication will compromise the outcome or integrity of the study.

Patients/caregivers should be instructed about the importance of informing the clinic staff of the use of any drugs or remedies (whether prescribed, over-the-counter, or illicit) before and during the course of the study. Information regarding any concomitant drugs taken by a patient during the course of the study and the reason for use will be recorded in the source documents and in the concomitant medication CRF.

Pharmacokinetic data indicate that no ataluren dose adjustment is required when ataluren is co-administered with systemic corticosteroids (deflazacort, prednisone, or prednisolone), and no corticosteroid dose adjustments are required when they are co-administered with ataluren. Co-administration of systemic corticosteroids with ataluren may cause more frequent instances of hypertension than does systemic corticosteroid use alone (without ataluren). However, the blood pressure data available to date are not unequivocal about any contributory role of ataluren in development of hypertension in patients who are taking corticosteroids.

7.1.4. Drugs Metabolized by Cytochrome P450 Enzymes

As the primary route of ataluren metabolism is via glucuronidation by UGT1A9, clinically significant interactions between ataluren and co-administered drugs metabolized by cytochrome P450 enzymes (CYPs) are unlikely. In particular, ataluren is not an inhibitor of CYP1A2, CYP2B6, CYP2C19, CYP2D6, and CYP3A4/5, and does not have induction potential on the major CYP enzymes.

In vitro, ataluren is a weak inhibitor of CYP2C8 and CYP2C9, but in vivo drug-drug interactions mediated by these enzymes are not expected according to the criteria described in the EMA guideline on the investigation of drug interactions [EMA 2012]. As an added measure of safety, investigators should pay specific attention to use of drugs that are known substrates of these enzymes, particularly when such drugs may have a low therapeutic index.

Drugs that are metabolized by CYP2C8 or CYP2C9 that have low therapeutics indices (in particular, paclitaxel for CYP2C8 and coumarin anticoagulants [eg, warfarin], phenytoin, or tolbutamide for CYP2C9) may be of particular concern and patients who require the use of these drugs will not be enrolled to the study. Coumarin anticoagulants are cleared by CYP2C9 and increases in plasma concentrations of coumarin anticoagulants may result in serious clinical consequences. For patients who require anticoagulation during the study, use of an alternative form of anticoagulation (eg, fractionated heparin) should be considered. Phenytoin is metabolized by CYP2C9 and concomitant use with ataluren may be of potential concern. For patients who require anticonvulsant therapy during the study, use of alternative anticonvulsant drugs should be considered. The metabolism of losartan to its active metabolite may, in part, be mediated by CYP2C9. However, concomitant use of losartan and inhibitors of CYP2C9 have not been examined. Because this drug does not have a narrow therapeutic window, the potential for mild to moderate changes in activity does not require a dose modification.

7.1.5. Other Potential Drug Interactions

Based on in vitro studies, ataluren is a substrate of UGT1A9 and breast cancer resistant protein (BCRP). Caution should be exercised when ataluren is co-administered with drugs that are inducers of UGT1A9 (eg, phenobarbital, rifampin), or inhibitors of BCRP (eg, cyclosporine, eltrombopag, geftinib).

In vitro data indicate that ataluren is an inhibitor of UGT1A9, organic anion transporter 1 (OAT1), organic anion transporter 3 (OAT3) and organic anion transporting polypeptide 1B3

(OATP1B3). Caution should be exercised when ataluren is co-administered with drugs that are substrates of UGT1A9 (eg, propofol, mycophenolate mofetil), OAT1, OAT3, or OATP1B3 (eg, oseltamivir, acyclovir, ciprofloxacin, captopril, furosemide, bumetanide, valsartan, pravastatin, rosuvastatin, atorvastatin, pitavastatin) because of the risk of increased concentration of these drugs.

The investigator is encouraged to consult the PTC medical monitor (or qualified designee) with questions relating to specific drugs and their potential for interactions with ataluren.

7.2. Non-Drug Therapy

7.2.1. Physical and Respiratory Therapy

There are neither restrictions nor prescriptions for physical or respiratory therapy during the study. Sites should use local best practices in providing physical therapy support for patients participating in the study. Respiratory care guidelines as suggested by the American Thoracic Society/European Thoracic Society should be followed [Miller 2005a, Miller 2005b]. If changes in the physical or respiratory therapy regimen are planned, sites are encouraged to initiate these changes prior to enrollment and to maintain the same general level of support throughout the duration of the study.

7.2.2. Dietary Restrictions

There are no specific dietary restrictions in the study.

7.2.3. Hydration

Because of the potential risk of renal dysfunction during periods of dehydration in patients receiving ataluren, it is important to encourage study patients to maintain adequate hydration throughout the study. Patients should be adequately hydrated prior to receiving any potentially nephrotoxic agents, and hydration status should be carefully monitored throughout the administration of any agent with nephrotoxic characteristics. Investigators should be particularly vigilant with patients who are experiencing nausea, vomiting, diarrhea, fever, or laboratory evidence of dehydration.

8. SCHEDULE OF EVENTS AND STUDY PARAMETERS

8.1. Schedule of Events

The proposed types and timing of data to be recorded are described in Table 3. Please see Section 8.2 for cross-referenced explanations of the study procedures described in the tables.

Study Period	Screening/ Treatment Per					Perio	bd		Post-Treatment	
Study Week (±7 days)	Day 1	12	24	36	48	60	72	84	End of Tx/ Premature D/C 96	4 Weeks Post-Tx
Visit	1	2	3	4	5	6	7	8	9	10
Informed consent	Х									
CFQ-R administration	Xa	Х	Х	Х	Х	Х	Х	Х	Х	
Vital signs	Xa	Х	Х	Х	Х	Х	Х	Х	Х	Х
Height	Xa	Х	Х	Х	Х	Х	Х	Х	Х	Х
Weight	Xa	Х	Х	Х	Х	Х	Х	Х	Х	Х
Physical examination	Xa				Х				Х	Х
Hematology	Xa	Х	Х	Х	Х	Х	Х	Х	Х	Х
Biochemistry	Xa	Х	Х	Х	Х	Х	Х	Х	Х	Х
Urinalysis	Xa	Х	Х	Х	Х	Х	Х	Х	Х	Х
Renal ultrasound	Xa				Х				Х	
12-lead ECG	Xa				Х				Х	Х
Study drug assignment	Х									
Drug dispensed	Х	Х	Х	Х	Х	Х	Х	Х		
Drug compliance		Х	Х	Х	Х	Х	Х	Х	Х	
Adverse events	Х	Х	Х	Х	Х	Х	Х	Х	Х	Х
Concomitant medication	Х	Х	Х	Х	Х	Х	Х	Х	Х	Х
Spirometry	Xa	Х	Х	Х	Х	Х	Х	Х	Х	Х
Respiratory event evaluation ^b	Xa	Х	Х	Х	Х	Х	Х	Х	Х	
P. aeruginosa in sputum	Xa	Х	Х	Х	Х	Х	Х	Х	Х	
Pharmacokinetics			Х		Х		Х		Х	

Table 3. Schedule of Events

^a Study procedure need not be performed if Day 1 is within 14 days of the end of study evaluations at Week 48 (Visit 8) of the preceding Phase 3 double-blind study (PTC124-GD-021-CF). If Day 1 is >14 days from the end of study visit, study procedure must be performed; however, it is not required to assess serum electrolytes, urine protein; urine creatinine ratio (spot sample), or urine blood (by dipstick).

^b Includes completion of the Respiratory Event Form.

° **Abbreviations**: D/C = discontinuation; ECG = electrocardiogram; F/U = follow up; Tx = treatment

8.2. Explanation of Study Procedures

8.2.1. Transition from the Phase 3 Study, Ataluren Treatment, and Follow-up Periods

Every effort should be made to conduct the Screening/Baseline visit (Visit 1) on the day of the End-of-Treatment visit (Visit 8/Week 48) of the Phase 3 double-blind study

(PTC124-GD-021-CF) to avoid interruption in treatment with study drug. Signature of the informed consent/assent document(s) for this study should be obtained after completion of the study procedures at the End-of-Treatment visit (Visit 8/Week 48) of the Phase 3 double-blind study (PTC124-GD-021-CF).

8.2.2. Screening/Baseline Visit (Visit 1)

Following signature of the informed consent/assent document(s), the patient will complete the necessary screening evaluations. It should be noted that results from safety laboratory tests from End-of-Treatment visit (Visit 8/Week 48) of the Phase 3 study (PTC124-GD-021-CF) are not

required to determine eligibility. Patients who have been confirmed to be eligible by the investigator for this extension study should complete all Screening/Baseline (Visit 1) study procedures. Most of the data collected during the End-of-Treatment visit (Visit 8/Week 48) of the Phase 3 study (PTC124-GD-021-CF) can be utilized for the baseline assessments (see footnote "a" of Table 3. If the Baseline visit (Visit 1) is not completed within 14 days of the End-of-Treatment visit (Visit 8/Week 48) of the Phase 3 study (PTC124-GD-021-CF), all study procedures should be performed; however, it is not required to assess serum electrolytes, urine protein; urine creatinine ratio (spot sample), or urine blood (by dipstick).

After the completion of the baseline study procedures, a site representative should access the IVR/IWR system and supply the necessary information to obtain ataluren dosing instructions. The patient will remain at the clinic until ataluren supply for the next 12 weeks has been dispensed and the patient/caregiver has been instructed regarding ataluren storage, preparation, and administration.

8.2.3. Treatment Visits during Study (Visits 2 through 9)

Each patient will subsequently return to the clinical research facility during Week 12 (Visit 2), Week 24 (Visit 3), Week 36 (Visit 4), Week 48 (Visit 5), Week 60 (Visit 6), Week 72 (Visit 7), Week 84 (Visit 8), and Week 96 (Visit 9).

8.2.4. End of Treatment

The patient will return to the clinical research facility at Week 96 (Visit 9) for the End-of-Treatment visit. If the patient discontinues prematurely (ie, before Week 96), the procedures that would normally be performed at Week 96 should be performed as a Premature-Discontinuation Visit before the patient leaves the study.

8.2.5. Post-Treatment Visits

All patients who discontinue study drug must return for a Post-Treatment Visit at the investigator site 4 weeks (\pm 7 days) after the last dose of study drug and the End of Treatment Visit, for final study-related evaluations. If the End-of-Treatment Visit occurs >4 weeks after the last dose of study drug, the Post-Treatment Visit does not need to be performed.

8.2.6. Informed Consent

The investigator or sub-investigator must inform each prospective patient of the nature of the study, explain the potential risks, and obtain written informed consent/assent from the patient and/or the parent/legal guardian prior to performing any study-related screening procedures. Patients will be re-consented with the appropriate age-related documents as needed, if required by local regulations.

8.2.7. Vital Signs

Vital signs (including systolic and diastolic blood pressure, pulse rate, pulse oximetry, and body temperature) will be monitored at Screening/Baseline on Visit 1, Week 12 (Visit 2), Week 24 (Visit 3), Week 36 (Visit 4), Week 48 (Visit 5), Week 60 (Visit 6), Week 72 (Visit 7), Week 84 (Visit 8), Week 96 (Visit 9 - End-of-Treatment/Premature Discontinuation), and at the Post-Treatment visit (4 weeks post discontinuation of study drug). The pulse rate and blood pressure determinations will be performed with the patient in a sitting position after a 5-minute rest.

8.2.8. Height, Weight, and Physical Examination

Height (in cm) and weight (in kg) will be measured at Screening/Baseline on Visit 1, Week 12 (Visit 2), Week 24 (Visit 3), Week 36 (Visit 4), Week 48 (Visit 5), Week 60 (Visit 6), Week 72 (Visit 7), Week 84 (Visit 8), Week 96 (Visit 9 - End-of-Treatment/Premature Discontinuation), and at the Post-Treatment visit (4 weeks post discontinuation of study drug).

A full physical examination (including general appearance, head, eyes, ears, nose, mouth, throat, heart, thyroid, chest and lungs, abdomen, extremities, neuromuscular system, skin, and lymph nodes) will be conducted at Screening/Baseline (Visit 1), Week 48 (Visit 5) and Week 96 (Visit 9 – End of Treatment/Premature Discontinuation) visit.

Physical exams may also be performed at any time during the study as clinically indicated.

8.2.9. Pregnancy

Serum beta chorionic gonadotropin (β -HCG) will be measured at all study visits (females only).

8.2.10. Hematology Laboratory Assessment

Hematology laboratory assessments will include white blood cell count with differential, hemoglobin, hematocrit, mean corpuscular volume, mean corpuscular hemoglobin, mean corpuscular hemoglobin concentration, total red cell count with morphology, and platelet count. These parameters will be measured at Screening/Baseline on Visit 1, Week 12 (Visit 2), Week 24 (Visit 3), Week 36 (Visit 4), Week 48 (Visit 5), Week 60 (Visit 6), Week 72 (Visit 7), Week 84 (Visit 8), Week 96 (Visit 9 - End-of-Treatment/Premature Discontinuation), and at the Post-Treatment visit (4 weeks post discontinuation of study drug). Hematology parameters will be analyzed by the central laboratory. The Central Laboratory Manual should be consulted for collection, processing, and shipping details.

8.2.11. Serum Biochemistry Laboratory Assessment

Biochemistry laboratory assessments will include sodium, potassium, chloride, bicarbonate, blood urea nitrogen, creatinine, magnesium, calcium, phosphorus, uric acid, glucose, total protein, albumin, globulin, albumin:globulin ratio, bilirubin (total, direct and indirect), creatine kinase (CK), lactate dehydrogenase (LDH), alanine aminotransferase (ALT), aspartate aminotransferase (AST), gamma glutamyl transferase (GGT), alkaline phosphatase, total cholesterol, high-density lipoprotein (HDL), low-density lipoprotein (LDL), triglycerides, and cystatin C. These parameters will be measured at Screening/Baseline on Visit 1, Week 12 (Visit 2), Week 24 (Visit 3), Week 36 (Visit 4), Week 48 (Visit 5), Week 60 (Visit 6), Week 72 (Visit 7), Week 84 (Visit 8), Week 96 (Visit 9 - End-of-Treatment/Premature Discontinuation), and at the Post-Treatment visit (4 weeks post discontinuation of study drug). Patients should have fasted for at least 8 hours prior to blood collection. Biochemistry parameters will be analyzed by the central laboratory. The Central Laboratory Manual should be consulted for collection, processing, and shipping details.

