11.4.5. Primary Variables

11.4.5.1 *Adverse Event*

Adverse events will be classified using the MedDRA classification system. The severity of adverse events will be graded according to the CTCAE, Version 3.0, whenever possible.

A treatment-emergent adverse event is defined as an adverse event that occurs or worsens in severity in the period extending from the day of a subject's first ataluren dose in this study to 4 weeks after the last ataluren dose in this study.

The number and percentage of subjects experiencing a specific adverse event will be tabulated by body system and MedDRA term. A subject having the same event more than once will be counted only once. Adverse events will be summarized by worst CTCAE grade within a subject. Exposure-adjusted incidence rate will be reported.

Adverse events classified as CTCAE Grade 3 or higher; study-drug-related events; hepatic, and renal events leading to special diagnostic evaluations; events leading to discontinuation from treatment; SAEs; and AESIs will be considered with special attention.

11.4.5.2 *Laboratory Data*

Hematological, serum biochemistry, urine data, and their changes (only for continuous laboratory parameters) from baseline will be summarized descriptively for each visit. Hematological, serum biochemistry, and urine data will be graded according to CTCAE severity grade when applicable. For parameters for which a CTCAE scale does not exist, the frequency of subjects with values below, within, and above the normal ranges will be summarized. Summary tables will be presented for each relevant assay to show the number of subjects by severity grade with corresponding percentages. Subjects will be characterized only once for a given assay, based on their worst severity grade observed during the time period of interest.

Separate listings and tables will be created for assessment of hepatic and renal parameters.

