14.2.9. Actions to be Taken in Response to Safety Signals

The intent of the recommendations to investigators regarding response to safety signals is to encourage a medically appropriate and consistent approach to adverse events and laboratory abnormalities. While specific monitoring, diagnostic testing, and supportive care measures must be instituted based on the clinical judgment of the investigator, investigators are encouraged to contact the PTC Therapeutics medical monitor (or qualified designee) to obtain guidance and to ascertain whether similar events are being seen at other investigator sites. The availability of advice from medical experts retained by PTC Therapeutics is intended to provide a uniformly high level of consultation in support of the investigators and the PTC Therapeutics medical monitor.

The dose interruption and modification provisions are designed to balance a primary concern for patient safety with the potential for observing efficacy in circumstances under which a patient experiencing an adverse event may still be able to continue on therapy at a lower study drug dose. Interruption of therapy is advocated as the primary response in order to determine reversibility of the adverse finding.

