In addition, in clinical trials in nmDMD the adverse-event profile of ataluren was comparable to that of placebo. In the double-blind Phase 2b study of nmDMD, six patients – all receiving corticosteroids - had hypertension (or increased blood pressure) reported as adverse events (0 for ataluren 20-, 20-, 40-mg/kg, 5 for ataluren 10-, 10-, 20-mg/kg, and 1 for placebo), although similar events were not seen in the nmCF studies. Mean total cholesterol and triglycerides were in the upper range of normal at baseline and increased, reaching borderline high or high values. The values tended to stabilize early in the study and did not increase further with continued treatment. Small increases in mean serum creatinine, BUN, and cystatin C were observed. Similarly, the values tended to stabilize early in the study and did not increase further with continued treatment.

Collectively, the safety data from clinical trials demonstrate that ataluren has a favorable safety profile for the treatment of patients with nmCF.

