4.10.2. Clinical Laboratory Evaluations

Hematology laboratory assessments will include white blood cell count with differential, hemoglobin, hematocrit, mean corpuscular volume, mean corpuscular hemoglobin, mean corpuscular hemoglobin concentration, total red cell count with morphology, and platelet count. These parameters will be measured at all study visits.

Biochemistry laboratory assessments will include sodium, potassium, chloride, bicarbonate, blood urea nitrogen, creatinine, magnesium, calcium, phosphorus, uric acid, glucose, total protein, albumin, globulin, albumin:globulin ratio, bilirubin (total, direct and indirect), creatine kinase (CK), lactate dehydrogenase (LDH), alanine aminotransferase (ALT), aspartate aminotransferase (AST), gamma glutamyl transferase (GGT), alkaline phosphatase, total cholesterol, high-density lipoprotein (HDL), low-density lipoprotein (LDL), triglycerides, and cystatin C. These parameters will be measured at all study visits. Ideally, subjects should have fasted for at least 8 hours prior to blood collection.

Urinalysis assessments will include pH, specific gravity, glucose, ketones, blood, protein, creatinine, urobilinogen, bilirubin, nitrite, and leukocyte esterase. These parameters will be measured at all study visits.

Hematology, serum biochemistry, and urinalysis data and their changes from baseline (only for continuous laboratory parameters) will be summarized by visit. Maximal and minimal change from baseline in each parameter will also be summarized.

Shift tables for hematology, serum biochemistry, and urinalysis will also be presented showing change in CTCAE severity grade from baseline to each visit. For parameters for which a CTCAE scale does not exist, shift tables will be presented showing change in results from baseline (normal, low, and high [or abnormal]) to each visit (normal, low, and high [or abnormal]).

Frequency tables will be presented for safety monitoring parameters to show the number and percentages of subjects by severity grade categories defined in Table 2. If a CTCAE grade does not exist, abnormal results will be summarized by protocol-defined thresholds as noted in Table 2. Subjects will be characterized only once for a given assay, based on their worst severity grade observed during the time period of interest.

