5.2. Analysis Visits

Analysis visits are the scheduled visits in the protocol, unless specified otherwise. They are not derived via visit window mapping. Baseline is derived as noted in Section 5.1. Final Visit is derived as the last non-missing on-treatment visit during the study for each subject and included into the by-visit summary analyses. Early termination visit should also be derived as the visit right after the non-missing scheduled visit. For example, if the subject discontinued after Week 12, the early termination visit should be derived as Week 24.

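### Post-Treatment laboratory values are compared only with extension baseline, pooled over prior Study 021 treatment, so the planned summary cannot show whether renal markers recover off drug

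*Protocol*

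**What the plan says.** - **Collection.** Protocol 8.2.11 lists the serum biochemistry sampling times and ends with "and at the Post-Treatment visit (4 weeks post discontinuation of study drug". Sections 8.2.10 and 8.2.12 do the same for hematology and urinalysis.
- **Exception.** Protocol 8.2.5 states: "If the End-of-Treatment Visit occurs >4 weeks after the last dose of study drug, the Post-Treatment Visit does not need to be performed".
- **Analysis.** Protocol 11.4.5 says that "changes (only for continuous laboratory parameters) from baseline will be summarized descriptively for each visit". SAP 4.10.2 says that the laboratory "data and their changes from baseline (only for continuous laboratory parameters) will be summarized by visit", and adds maximal and minimal change from baseline and shift tables from baseline to each visit. SAP 5.4 defines absolute and relative change from Baseline only.
- **Baseline.** SAP 5.1 takes the last valid value on or before the first extension dose, or Study 021 Week 48 if that is missing. SAP 2.1 says the transition is built to avoid a treatment gap. Entrants completed either placebo or ataluren (Protocol 4.2).
- **Last on-drug value.** SAP 5.2: "Final Visit is derived as the last non-missing on-treatment visit during the study for each subject". It goes into the by-visit tables but is not used as a reference for later values.
- **Prior treatment.** SAP 4.11 reports FEV1, exacerbations and FVC overall and by Study 021 arm. SAP 4.10.2 has no such split.

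**The concern.** Renal safety is the main safety question the protocol raises. Protocol 14.2.4 reports renal findings in mice with no NOAEL, and seven renal serious adverse events in Study 009 (3 + 3 + 1), all on ataluren. The reassurance it offers is largely reversibility: the mouse findings reversed partly or fully from 2 to 6 weeks after dosing stopped, and the creatinine elevations resolved over days to weeks. Protocol 14.2.9 gives reversibility as the reason for interrupting drug: "Interruption of therapy is advocated as the primary response in order to determine reversibility of the adverse finding".

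The Post-Treatment visit falls within that 2-to-6-week window and is the one off-drug laboratory assessment scheduled for all patients who stop, apart from the 8.2.5 exception. The planned summary, however, refers these values to a baseline that means different things in the two prior arms, and then pools the arms. A reader of the Post-Treatment row could take a mean change near zero as full recovery, or a negative one as an improvement on an untreated state. Neither reading would be safe.

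**Working it through.** The documents give no effect size, SD or power figure for renal markers, so there is no planned figure to reproduce. The check is algebra on the planned summary, followed by an illustration of precision.

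**Assumptions (not in the documents).** d = mean on-drug shift in a marker, stable and equal in both prior arms. r = fraction of d reversed 4 weeks after the last dose. p = share of patients previously on ataluren, taken as 0.4 to 0.6.

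**Step 1: change from extension baseline to the Post-Treatment visit.**
- Ex-ataluren (baseline already shifted by d): (1 − r)d − d = −r·d
- Ex-placebo (baseline unshifted): (1 − r)d − 0 = (1 − r)d
- Pooled: p(−r·d) + (1 − p)(1 − r)d = (1 − p − r)d

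**Step 2: change from the last on-treatment value to the Post-Treatment visit.** In both arms: (1 − r)d − d = −r·d, for any p.

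| Mean change | r = 0 | r = 0.5 | r = 1 |
|---|---|---|---|
| Pooled vs baseline, p = 0.4 | +0.6d | +0.1d | −0.4d |
| Pooled vs baseline, p = 0.5 | +0.5d | 0 | −0.5d |
| Pooled vs baseline, p = 0.6 | +0.4d | −0.1d | −0.6d |
| Paired vs last on-treatment, any p | 0 | −0.5d | −d |

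At p = 0.5 the pooled change is (0.5 − r)d, so a zero means half reversal.

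**Step 3: can the by-visit rows be subtracted?** The pooled Final Visit row averages (1 − p)d. Post-Treatment minus Final Visit is (1 − p − r)d − (1 − p)d = −r·d, but only if the same patients are in both rows. The paired standard error cannot be obtained from the two rows. Treating them as independent inflates the interval by 1/√(1 − ρ), where ρ is the within-patient correlation: 1/√0.5 = 1.4 at ρ = 0.5 and 1/√0.1 = 3.2 at ρ = 0.9.

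In SD units at n = 200 (Protocol 5.1 expects about 200 patients), the paired half-width is 1.96·√(2(1 − ρ)/n) = 0.139, 0.107 and 0.062 for ρ = 0.5, 0.7 and 0.9, against 1.96·√(2/200) = 0.196 unpaired.

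**Step 4: precision for creatinine.** Half-width = t(0.975, n − 1)·SD/√n, with an assumed SD of the within-patient difference:
- n = 200, SD 0.08 mg/dL: 0.011
- n = 150, SD 0.10 mg/dL: 0.016
- n = 100, SD 0.15 mg/dL: 0.030

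**Step 5: which values are off drug?** By Protocol 8.2.5, an End-of-Treatment visit more than 4 weeks after the last dose stands in for Visit 10. SAP 5.2 maps an early termination visit to the next scheduled treatment week. An off-drug value can therefore sit in an on-treatment row unless it is classified by days since last dose.

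**The case against.** **The values are analysed.** Analysis visits are the scheduled visits, so Post-Treatment values are tabulated against baseline, and the Final Visit row appears in the same tables. Protocol 11.4.5 also promises separate hepatic and renal tables and listings, and SAP section 6 does not remove them. This stands: a reader might infer that the off-drug data go unanalysed, and that is wrong. What is missing is a specified within-patient contrast and a split by prior arm. The separate renal tables are promised without a stated reference value.

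**The visit is not described as a reversibility check, and it is not the only off-drug information.** Protocol 8.2.5 describes final evaluations. Protocol 7.1.2 requires creatinine and BUN at least twice weekly while ataluren is interrupted for nephrotoxic antibiotics. Protocol 9.7 follows patients withdrawn for an adverse event until laboratory results normalise or the event stabilises. A creatinine rise that triggers a work-up is recorded as an adverse event with an outcome. All of this stands. These data cover selected patients, however, and no summary of reversal is specified from them.

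**A mean shift in nmCF is not shown.** The sentence "Small increases in mean serum creatinine, BUN, and cystatin C were observed" (Protocol 15.3) is in a paragraph about nmDMD. For nmCF, Protocol 14.2.4 reports no clinically meaningful creatinine difference between arms at Week 48 of Study 009. This stands, so d is purely notional here.

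**Stopping on the sponsor's decision does not make the contrast control-free.** SAP 2.1 gives no count of patients still on drug. The bar on IV nephrotoxic antibiotics applies to use together with ataluren, so co-medication may change once drug stops.

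**All analyses are descriptive (SAP 4.2) and the study was ended early.** True, and the addition would be descriptive too.

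**Conclusion.** The point holds in a limited form. SAP 4.10.2 uses extension baseline as its only reference for Post-Treatment laboratory values and pools over prior treatment, so the resulting mean change does not measure recovery. Under the stated assumptions it is (1 − p − r)d, against −r·d for the paired change. The last on-treatment value that the better comparison needs is already derived.

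The algebra assumes a stable shift of equal size in both arms. The size of d, the prior mix, the SDs, the correlations and the number of pairs are all assumptions. The word normally matters too: Protocol 7.1.2 foresees gaps of more than one month between the studies, so some ex-ataluren baselines may be off drug, which mixes the reference further.

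The documents do not support saying that off-drug values are ignored, that Visit 10 is the study's designated or sole test of reversibility, that ataluren is known to shift mean renal markers in nmCF, or that the on/off contrast can be interpreted without regard to other changes at drug stop. The adverse-event analyses are unaffected.

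**What to change.** Amend SAP 4.10.2 before database lock, which SAP section 1 allows. For creatinine, cystatin C, BUN and the other Table 2 parameters:

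1. Present by-visit laboratory changes by preceding Study 021 treatment as well as overall, as SAP 4.11 does for FEV1.
2. Add the paired change with 95% CI, and a category shift, from the last on-treatment value to the Post-Treatment value, by prior arm and overall. State the number of pairs.
3. Classify values as on or off drug by actual days since the last dose, so that late End-of-Treatment visits and remapped early termination visits are placed correctly.
4. Do not use the worst on-treatment value as the reference. Regression to the mean would produce apparent recovery even with no drug effect.
5. Label the result descriptive, note that antibiotic use may change after drug is stopped, and show separately the patients stopped by the sponsor's termination.

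The cost is a few extra tables and one derivation from data already collected, with no new visits or samples.
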